6.12.4. Other Secondary and Exploratory Efficacy Analyses

Other secondary and exploratory efficacy measures will use the efficacy estimand and will be summarized by treatment and nominal visit. Missing data will not be explicitly imputed and assessments are not subject to type 1 error rate control. Some parameters may be log transformed, if necessary.

Table GPHD.6.2. Secondary and Exploratory Efficacy Analyses not Controlled for Type I Error

| Objective | Relative to the efficacy measure: | Analysis Conducted in a manner similar to section: | Additional Information |
|--|--|--|--|
| Secondary Analyses | | | |
| To evaluate superiority of tirzepatide (5 mg, 10 mg, and/or 15 mg) QW to insulin lispro (U100) at 52 weeks in: | Proportion of participants achieving an HbA1c target value of <7% (53 mmol/mol) | 6.12.2.3 | None |
| To evaluate superiority of tirzepatide (pooled cohort of 5 mg, 10 mg, and 15 mg) QW to insulin lispro (U100), And to evaluate superiority of tirzepatide 5 mg, 10 mg, and/or 15 mg QW to insulin lispro (U100) at 52 weeks in: | Proportion of participants achieving an HbA1c target value of $\leq 6.5\%$ (48 mmol/mol) | 6.12.2.3 | None |
| | Mean change in fasting serum glucose (central laboratory) from baseline | 6.12.1.1 | Use baseline HbA1c category ($\leq 8.5\%$, $>8.5\% [\leq 69, >69 \text{ mmol/mol}]$) in place of baseline HbA1c. Use baseline FSG as a covariate. |
| | Change from baseline in 7-point self-monitored blood glucose (SMBG) profiles | 6.12.1.1 | Use baseline SMBG as a covariate. LSM estimates at 52-weeks will be summarized by treatment and 7-points. |

| Objective | Relative to the efficacy measure: | Analysis Conducted in a manner similar to section: | Additional Information |
|-----------|---|---|--|
| | | | In addition to the analyses on each of the 7-points, similar analyses will be done for the 2-hour morning, midday, and evening meal excursions, the mean of all meals 2-hour excursion, the mean of all 7-point measurements, the mean of all pre-meal measurements, and the mean of all 2-hour postprandial measurements. |
| | Proportion of participants who achieved HbA1c target value of <7.0% (53 mmol/mol) without hypoglycemia (confirmed glucose <54 mg/dL [3.0 mmol/L] or report of severe hypoglycemia) | 6.12.2.3 | Severe hypoglycemia follows ADA level 3 definition. |
| | Proportion of patients who achieved weight loss of $\geq 5\%$, from baseline | 6.12.2.3 | Use baseline HbA1c category ($\leq 8.5\%$, $>8.5\% [\leq 69, >69 \text{ mmol/mol}]$) as in place of baseline HbA1c. Use baseline weight as a covariate. |
| | Mean change from randomization in SF-36v2 acute form Physical Component summary score Mental Component summary score Physical Functioning domain score General Health domain score Vitality domain score Role-Physical domain score Bodily Pain domain score | 6.12.1.2 | Use ANCOVA. Use baseline HbA1c category ($\leq 8.5\%$, $>8.5\% [\leq 69, >69 \text{ mmol/mol}]$) as in place of baseline HbA1c. Use corresponding baseline score as a covariate. |

| Objective | Relative to the efficacy measure: | Analysis Conducted in a manner similar to section: | Additional Information |
|--|---|---|---|
| | Social Functioning domain score Role-Emotional domain score Mental Health domain score | | |
| Exploratory Objectives | | | |
| To evaluate superiority of tirzepatide (pooled cohort of 5 mg, 10 mg, and 15 mg) QW to insulin lispro (U100) at 52 weeks in: | Change from baseline in lipid parameters (Total-Cholesterol, HDL-C, LDL-C, VLDL-C, TG) | 6.12.1.1 | Use baseline HbA1c category ($\leq 8.5\%$, $>8.5\% [\leq 69, >69 \text{ mmol/mol}]$) in place of baseline HbA1c. Use corresponding baseline lipid parameter as a covariate |
| | Change from baseline in waist circumference | 6.12.1.1 | Use baseline HbA1c category ($\leq 8.5\%$, $>8.5\% [\leq 69, >69 \text{ mmol/mol}]$) in place of baseline HbA1c. Use baseline waist circumference as a covariate |
| | Change from baseline in BMI | 6.12.1.1 | Use baseline HbA1c category ($\leq 8.5\%$, $>8.5\% [\leq 69, >69 \text{ mmol/mol}]$) in place of baseline HbA1c. Use baseline BMI as a covariate. |

| Objective | Relative to the efficacy measure: | Analysis Conducted in a manner similar to section: | Additional Information |
|-----------|--|--|---|
| | Change from baseline in patient reported outcomes: APPADL, IW-SP, EQ-5D-5L | 6.12.1.2 | Use ANCOVA. Use baseline HbA1c category ($\leq 8.5\%$, $>8.5\% [\leq 69, >69 \text{ mmol/mol}]$) as a fixed effect. Use corresponding baseline patient outcome score as a covariate. |

Abbreviations: ADA = antidrug antibodies; ANCOVA = analysis of covariance; APPADL = Ability to Perform Physical Activities of Daily Living; BMI = body mass index; FSG = fasting serum glucose; HbA1c = hemoglobin A1c; HDL-C = high-density lipoprotein-cholesterol; IW-SP = Impact of Weight on Self-Perceptions Questionnaire; LDL-C = low-density lipoprotein-cholesterol; LSM = least squares mean; QW = once-weekly; SF-36v2 = Short-Form-36 Health Survey Version 2; TG = triglycerides; VLDL-C = very low-density lipoprotein.

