Comparisons among treatments relative to the proportion of participants achieving the HbA1c target value of <7.0% (53 mmol/mol) at the 52-week visit will be conducted using a logistic regression analysis with terms of treatment, country, metformin use (Yes or No), and baseline HbA1c as a covariate. In the analysis of participants achieving the HbA1c target value relative to the “efficacy” estimand, subjects with missing values at the 52-week visit will be excluded. In the analysis of participants achieving the HbA1c target value relative to the “treatment-regimen” estimand, missing values at the 52-week visit will be imputed based on observed data at respective visits from participants in the same treatment arm who had their efficacy assessed after early discontinuation of study intervention and/or initiation of rescue medication. The analysis will be conducted with multiple imputations and statistical inference over multiple imputations will be guided by the method proposed by Rubin.³³

Analyses of actual and change from baseline in PRO scores will be conducted using linear models with baseline PRO scores, treatment, and other factors that may be considered relevant. These variables will be specified in the SAP.

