| Figure GPHD.5.1. | Illustration of study design for clinical protocol I8F-MC-GPHD..... | 13 |
| Figure GPHD.5.2. | Flowchart to ascertain need for insulin glargine (U100) optimization..... | 15 |
| Figure GPHD.6.1. | Type 1 Error control strategy for primary and key secondary efficacy endpoints..... | 29 |

Table of Contents

| Appendix | | Page |
|-----------------|--|-------------|
| Appendix 1. | Searching Criteria for Adverse Events of Special Interest..... | 50 |

3. Revision History

The first version of the statistical analysis plan (SAP) was approved prior to First Patient Visit (FPV).

The second version is approved before the final database lock. The following represent major changes made for the second version:

1. Updated definition of analysis set. For consistency with SURPASS 1-5 trials, exclude patients discontinuing study drug due to inadvertent enrollment from efficacy analyses.
2. Updated baseline definition as time is not collected in GPHD eCRF.
3. Missing data imputation: Modified the definition of “retrieved dropouts”.
4. Updated analysis used for hemoglobin A1c (HbA1c) and weight loss threshold analyses.
5. Change in alpha recycling for type 1 error rate control.
6. Removed ‘The patient recovered/ resolved with sequelae’ from Severe hypoglycemia requiring hospitalization, documented medical help, or is life threatening as this criteria alone will not be sufficient to meet additional criteria.
7. Removed section on Anti-Drug Antibodies as it was not collected for all patients.
8. Added section to assess SARS-CoV-2 (COVID-19) impact.

4. Study Objectives

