6.1. Populations for Analyses

For purposes of analysis, [Table GPHD.6.1](#) defines the following analysis populations/data sets.

Table GPHD.6.1. Analysis Populations/Data Sets

| Population/Data Set | Description |
|---|--|
| Screened population | All participants who sign informed consent |
| Enrolled population | All participants who are exposed to at least 1 dose of insulin glargine (U100) after Visit 2 |
| Randomized population | All participants who are randomly assigned a treatment arm |
| Safety Population | All randomly assigned participants who are exposed to at least 1 dose of study drug (tirzepatide or insulin lispro [U100]). |
| Modified intention-to-treat (mITT) population | All randomly assigned participants who are exposed to at least 1 dose of study drug (tirzepatide or insulin lispro [U100]), excluding inadvertently enrolled participants who have discontinued study drug for that reason. |
| Lead-in analysis set (LAS) | Data obtained during Study Period I, after first dose of insulin glargine (U100) after Visit 2 and prior to the first dose of tirzepatide or insulin lispro (U100) (or Visit 6 date if the dose date is missing). |
| Efficacy analysis set (EAS) | Data obtained during Study Period II from the mITT population, excluding data after initiating rescue antihyperglycemic medication or early discontinuation of study drug (tirzepatide: last dose date + 7 days; insulin lispro (U100): last dose date). |
| Full analysis set (FAS) | All available data obtained during Study Period II, regardless of adherence to study drug or initiation of rescue antihyperglycemic medication. |
| Safety analysis set (SS) | All available data obtained during Study Periods II and III regardless of adherence to study drug or initiation of new antihyperglycemic medication. |

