6.4. Handling of Dropouts or Missing Data

For the primary and secondary efficacy endpoint analyses relative to treatment-regimen estimand and subject to type 1 error rate control, data for participants with missing values at the 52-week visit will be imputed based on the method described in Section 6.12.1.3. For analysis relative to efficacy estimand, missing values will be considered missing at random. Unless specified otherwise, imputation of missing data will be limited to primary and key secondary efficacy endpoint analyses. Any other secondary or exploratory efficacy parameter values or safety laboratory values that are missing will not be explicitly imputed.

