6.12.2.3. Analyses of Binary Outcomes

The proportion of patients achieving HbA1c values $<7.0\%$ at the 52-week visit relative to the “efficacy” estimand will be conducted utilizing data from the EAS from baseline through the 52-week visit with the aid of a logistic regression. Missing HbA1c data were imputed using all the available data in the same treatment using fully conditional specification regression method. The missing data is imputed as a continuous outcome. Statistical inference over multiple imputations will be guided by Rubin (1987)

The analysis relative to the “treatment-regimen” estimand will be conducted utilizing HbA1c data in the FAS at baseline and at the 52-week visit with the aid of a logistic regression using multiple imputation of missing HbA1c data at the 52-week visit (see Section 6.12.1.3 for details) using retrieved dropouts.

After the different missing imputation methods for the “efficacy estimand” and the “treatment-regimen” estimand, the imputed values will then be dichotomized into binary outcomes based on cutoff values. The logistic regression will include model terms of treatment, country/pooled country, and baseline metformin use (Yes/No) as fixed effects, and baseline HbA1c as a covariate. The treatment term will include tirzepatide 5 mg, 10 mg, and 15 mg and insulin lispro (U100). A linear contrast, averaging estimates from individual tirzepatide doses, will be used to estimate the proportion of patients achieving HbA1c $<7.0\%$ for the combined tirzepatide doses. Statistical inference over multiple imputations will be guided by Rubin (1987).

6.12.3. Type 1 Error Rate Control Strategy for Primary and Key Secondary Efficacy Analyses

Since they are intended for different purposes, no type 1 error rate adjustments will be made for conducting analyses relative to “efficacy” and “treatment-regimen” estimands. For analyses

within each estimand, the type 1 error control strategy for evaluation of the primary and key secondary objectives is illustrated in [Figure GPHD.6.1](#).

The primary and key secondary objective hypotheses are as follows:

- $H_{p,1}$: The pooled cohort of tirzepatide (5 mg, 10 mg, and 15 mg) QW is noninferior to insulin lispro (U100) TID, relative to the mean change in HbA1c from baseline to 52 weeks.
- $H_{p,2}$: The pooled cohort of tirzepatide (5 mg, 10 mg, and 15 mg) QW is superior to insulin lispro (U100) TID, relative to mean change in HbA1c from baseline to 52 weeks.

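### For HbA1c below 7% without hypoglycemia, the SAP gives conflicting missing-data rules, and the rule its table cites judges the two components over different time spans

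*SAP*

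**What the plan says.** The composite, listed in SAP Table GPHD.6.2 as "Proportion of participants who achieved HbA1c target value of <7.0% (53 mmol/mol) without hypoglycemia", is an additional secondary endpoint. It requires HbA1c below 7.0% at Week 52 and no confirmed glucose below 54 mg/dL or severe hypoglycemia.

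- **Estimand and data.** SAP 6.12.4 states: "Other secondary and exploratory efficacy measures will use the efficacy estimand". The matching efficacy analysis set (EAS, SAP Table GPHD.6.1) is Study Period II data, "excluding data after initiating rescue antihyperglycemic medication or early discontinuation of study drug".
- **Rule against imputation.** SAP 6.12.4 adds: "Missing data will not be explicitly imputed and assessments are not subject to type 1 error rate control". SAP 6.4 agrees: "Any other secondary or exploratory efficacy parameter values or safety laboratory values that are missing will not be explicitly imputed".
- **Rule for imputation.** The composite's row in Table GPHD.6.2 says the analysis is done in a manner similar to 6.12.2.3. For the efficacy estimand, that section says: "Missing HbA1c data were imputed using all the available data in the same treatment using fully conditional specification regression method". The imputed values are then dichotomized.
- **Revision history (SAP Section 3, item 4).** "Updated analysis used for hemoglobin A1c (HbA1c) and weight loss threshold analyses".
- **Protocol 9.4.3.2.** For HbA1c below 7% under the efficacy estimand, "subjects with missing values at the 52-week visit will be excluded". It does not address the composite.
- **Hypoglycemia component.** The row's only extra instruction fixes the definition of severe hypoglycemia. It gives no observation window and no rule for incomplete follow-up.
- **Follow-up.** Under Protocol 7.1, participants who stop study drug stay in the study and complete all visits. Under Protocol 8.3.6.1, hypoglycemia is collected from Visit 2 to the last study visit.

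**The concern.** An endpoint of target reached without an event needs both parts judged over the same period. If HbA1c is completed to Week 52 while hypoglycemia is counted only until the participant leaves the EAS, short exposure counts as absence of hypoglycemia. A participant who stops drug at Week 8 with no event and receives an imputed HbA1c of 6.8% is a 52-week success on 8 weeks of hypoglycemia data.

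The resulting over-credit depends on how many participants leave the EAS in each arm, when they leave, and the arm's hypoglycemia rate. All three can differ between weekly tirzepatide and three-times-daily lispro. The trial's rationale is better control with less hypoglycemia than basal-bolus therapy, and this endpoint expresses that directly. SAP 6.12 says efficacy-estimand results are meant for publications. In an open-label trial, an unresolved choice between two written rules is better settled before the data are analyzed.

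**Working it through.** The documents give no figure for this endpoint, so there is nothing to reproduce. The calculation sizes the effect on the reading that 6.12.2.3 imputation applies and hypoglycemia is counted within the EAS only.

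**Inputs, all assumptions:** fraction leaving the EAS d = 10% (lispro), 15% (tirzepatide); probability of HbA1c below 7% P = 50%, 70%, the same for leavers as for others; 52-week hypoglycemia incidence H = 30-60%, 10-15%; constant hazard; exit week t = 8 to 26, the same in both arms.

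**Formula.** A leaver is event-free at exit with probability (1-H)^(t/52), against 1-H over 52 weeks. So

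over-credit = d × P × [(1-H)^(t/52) - (1-H)].

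**Central case** (t = 16, H = 50% vs 10%):
- Lispro: 0.10 × 0.50 × (0.808 - 0.500) = 1.5 points.
- Tirzepatide: 0.15 × 0.70 × (0.968 - 0.900) = 0.7 points.
- Full-period composite: 0.50 × 0.50 = 25% and 0.70 × 0.90 = 63%, a difference of 38 points. The error is 1.54 - 0.72 = 0.8 points, which shrinks the tirzepatide advantage. The standard error with 591 per group is √[(0.25×0.75 + 0.63×0.37)/591] = 2.7 points, so the error is about 0.3 of a standard error.

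**Range by arm:**

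| Arm | Smallest | Largest |
|---|---|---|
| Lispro | H=30%, t=26: 0.05 × (0.837 - 0.700) = 0.7 | H=60%, t=8: 0.05 × (0.869 - 0.400) = 2.3 |
| Tirzepatide | H=10%, t=26: 0.105 × (0.949 - 0.900) = 0.5 | H=15%, t=8: 0.105 × (0.975 - 0.850) = 1.3 |

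**Error in the difference** (lispro over-credit minus tirzepatide over-credit, same exit week, all incidences crossed):
- Lowest: 30% vs 15%, t = 8: 1.23 - 1.32 = -0.1 points. The tirzepatide advantage is slightly inflated.
- Highest: 60% vs 10%, t = 8: 2.34 - 0.88 = 1.5 points. The advantage shrinks.

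The sign therefore changes within the assumed ranges. If exit weeks also differed between arms, the extremes would widen to 0.68 - 1.32 = -0.6 and 2.34 - 0.51 = 1.8 points.

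**When the effect disappears:**
- *No imputation.* Leavers with no Week 52 EAS value drop out, and under the same assumptions there is no inflation.
- *Leavers with poor HbA1c.* Stopping raises success only if the leaver-to-completer ratio of HbA1c success exceeds (1-H)^(1-t/52). For exit at Week 26 this is √(1-H): 0.95 at H = 10%, 0.79 at 37% and 0.66 at 57%. The 37% and 57% are the rates that Protocol 2.1 cites from two basal-bolus studies, used here only for illustration because the event definition is not given.

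**The case against.** The strongest objection is that imputation is not settled. The sentence directly above the table rules it out, 6.4 agrees, the table says only that the analysis is similar to 6.12.2.3, and the protocol excludes missing Week 52 values for the simple HbA1c target. This stands: on that reading the inflation is gone. It does not end the matter, because the row still cites a section whose efficacy-estimand method is imputation. The revision item also names weight loss thresholds, and the 5% weight loss endpoint is analyzed only in this table. That makes the imputation reading the more plausible one.

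Two stronger inferences are tempting, and the documents support neither.

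- *That hypoglycemia after stopping is unobserved.* For participants who stop drug but stay in the study, it is collected and then excluded by the EAS. It is unobserved only after study withdrawal.
- *That stopping early always makes success more likely.* This needs imputed HbA1c success close to that of completers. Participants starting rescue after Week 24 for severe, persistent hyperglycemia (Protocol 8.3.6.2) are poor candidates for HbA1c below 7%.

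Constant hazard is also doubtful while doses are being escalated and titrated. It is fair to add that the endpoint is not type 1 error controlled, that the central-case error works against tirzepatide, and that hypoglycemia has its own analyses in SAP 6.13.2.1, including an optional rate model that adjusts for exposure. These points limit the importance but leave the gap in place.

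**Conclusion.** The concern holds in a conditional form. The SAP gives two incompatible missing-data rules for this composite and no window for its hypoglycemia component. If the cited section is followed, Week 52 HbA1c is paired with hypoglycemia judged only to drug stop or rescue, and event-free early stoppers are over-credited unless their imputed HbA1c success is well below that of completers.

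Under the assumed stopping, target and hypoglycemia rates, with constant hazard and a common exit week, the over-credit is 0.7 to 2.3 points for lispro and 0.5 to 1.3 points for tirzepatide. The difference is off by about -0.1 to 1.5 points. A reader might infer a systematic bias toward one arm, but the sign changes within the assumed ranges. The effect is small, on a secondary endpoint without type 1 error control. Priority: minor to moderate.

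**What to change.** 1. State in SAP 6.12.4 whether the 6.12.2.3 imputation governs this row, and align 6.4 and the table with that choice.
2. Define the hypoglycemia window as the same 52 weeks as the HbA1c component. If imputation governs, then within each imputation also draw hypoglycemia status for the weeks outside the EAS, given no event so far, from the same arm's on-treatment event rate. Form the composite afterwards and combine by Rubin's rules.
3. If imputation does not govern, say that participants without a Week 52 EAS HbA1c are excluded, and still state the window.
4. Add a sensitivity analysis using all hypoglycemia collected to Week 52, including after drug stop or rescue. It needs no new data.
5. Optionally, count incomplete EAS follow-up as non-achievement. This is a severe rule. With P = 50%, H = 37% and 10% leaving, it lowers the rate from 0.50 × 0.63 = 31.5% to 0.90 × 31.5% = 28.4%, a larger shift than any over-credit above, so it should not be the main analysis.

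The cost is a few SAP sentences and minor programming. Under item 2 the reported proportions would be slightly lower.

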6.13. Safety Analyses

Unless specified otherwise, safety assessments will be based on the Safety analysis Set (see [Table GPHD.6.1](#)). All events that occur between the date of first dose of study drug (ie, tirzepatide or insulin lispro [U100]) to the date of the patient's safety follow-up visit or the patient's end of study participation will be included, regardless of the adherence to study drug or initiation of rescue therapy. For assessing the benefit- risk profile through 52 weeks, selected safety analyses will be conducted by utilizing safety data from first dose through the date of the 52-week visit. Some safety analyses may be conducted after excluding data after initiation of new antihyperglycemic therapy. Additional safety analyses may be conducted using the LAS data set.

Unless specified otherwise, statistical assessment of homogeneity of the distribution of categorical safety responses among treatment arms (pooled cohort of tirzepatide doses and insulin lispro) will be conducted using Fisher exact test.

Unless specified otherwise, differences among treatment mean changes from baseline in continuous safety parameters at all scheduled visits will be assessed via an MMRM using REML. The model will include treatment, visit, treatment-by-visit interaction, country/pooled country, baseline HbA1c ($\leq 8.5\%$, $>8.5\% [\leq 69, >69 \text{ mmol/mol}]$), and baseline metformin use (Yes/No) as fixed effects, and baseline value of the safety parameter as a covariate. To model the covariance structure within patients, the unstructured covariance matrix will be used. If this model fails to converge, the covariance structures specified in Section [6.12.1.1](#) will be tested in order.

Unless specified otherwise, statistical summaries and analyses of safety assessments will be displayed in the following treatment order: individual tirzepatide doses (5 mg, 10 mg, 15 mg), pooled cohort of tirzepatide doses and insulin lispro (U100).

For selected safety parameters, time-to-first-event analysis via the Cox proportional hazards model may be conducted. For patients without an event, the “time-to-event” will be time (in days) from first dose to end of study participation. For patients experiencing the event, “time-to-first-event” will be the time (in days) from first dose to first occurrence of the event.

Where necessary, the rate of events will be analyzed using a generalized linear mixed-effects model assuming the number of events follow a negative binomial distribution, and including treatment as a fixed effect. The logarithm of days during the active treatment period will be adjusted as an offset to account for possible unequal treatment duration of follow-up between patients.

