5.3. Method of Assignment to Treatment

Approximately 1182 participants who meet all criteria for enrollment will be randomized to one of the study treatment arms at Visit 6. Assignment to treatment arms will be determined by a computer-generated random sequence using an interactive web response system (IWRS).

Participants will be randomized in a 1:1:1:3 ratio to receive 5 mg tirzepatide, 10 mg tirzepatide, 15 mg tirzepatide, or insulin lispro (U100). The randomization will be stratified by country, pre-randomization HbA1c concentration ($\leq 8.5\%$, $> 8.5\%$ [≤ 69 , > 69 mmol/mol]), and baseline metformin use (Yes/No).

6. A Priori Statistical Methods

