6.3. Adjustments for Covariates

The study is stratified by country, pre-randomization HbA1c ($\leq 8.5\%$, $> 8.5\% [\leq 69, > 69 \text{ mmol/mol}]$), and baseline metformin use (Yes/No). Where necessary to be included as a fixed effect, countries with fewer than 10 randomized participants will be pooled into one category (pooled country). For HbA1c related analyses, country/pooled country and baseline metformin use (Yes/No) will be used as fixed effects and baseline HbA1c as a covariate. For

other efficacy analyses, country/pooled country, baseline HbA1c ($\leq 8.5\%$, $>8.5\%$ [≤ 69 , >69 mmol/mol]), and baseline metformin use (Yes/No) will be used as fixed effects and respective baseline value as a covariate.

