6.5. Multicenter Studies

To investigate potential regional influences, country/pooled country will be used as a fixed effect in statistical analyses.

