For selected categories of hypoglycemia (including severe hypoglycemia and level 2 hypoglycemia/severe hypoglycemia), statistical summaries and analyses will exclude hypoglycemic events occurring after initiation of a new antihyperglycemic therapy. Incidence as well as rate per year of exposure will be provided by treatment.

Statistical summaries and analyses for severe hypoglycemia requiring hospitalization, documented medical help or is life threatening will be conducted using the Safety Analysis Set.

The incidence of hypoglycemic event will be analyzed using logistic regression with treatment, baseline HbA1c category, country/pooled country, and baseline metformin use (Yes/No) as fixed effects. The baseline incidence of hypoglycemic event during the insulin glargine (U100) optimization period and insulin optimization group may be adjusted as fixed effects. The rate of hypoglycemic episodes per patient year may be analyzed using a generalized linear mixed-effects model assuming the number of hypoglycemic episodes follows a negative binomial distribution with the mean modeled using country/pooled country, baseline metformin use (Yes/No), baseline HbA1c category, and treatment as fixed effects. The logarithm of days during the active treatment period will be adjusted as an offset to account for possible unequal treatment duration of follow-up between patients. The treatment term will include the combined tirzepatide arm and insulin lispro (U100). The baseline incidence/rate of hypoglycemic event during the

lead-in period and insulin optimization group may be adjusted as fixed effects. A nonparametric empirical model may be used to analyze the rate of hypoglycemic episodes if the event rate is low.

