6.13.2.2. Severe Persistent Hyperglycemia

A summary of initiation of rescue therapy in response to severe, persistent hyperglycemia will be provided by treatment. If there are a sufficient number of episodes, a time-to-first-event analysis for the initiation of rescue therapy will be conducted by treatment using a cox proportional regression model. For patients without an event the “time-to-event” will be time (in days) from first dose to end of study participation (study discontinuation or safety follow-up). A listing of patients initiating rescue therapy will be provided.

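### The SAP's default event-rate model for safety names treatment alone and omits the three randomisation factors, so rate-ratio intervals can be somewhat wider than necessary

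*SAP*

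**What the plan says.** SAP 5.3: "The randomization will be stratified by country, pre-randomization HbA1c concentration", with metformin use as the third factor. SAP 6.3 repeats this ("The study is stratified by country, pre-randomization HbA1c") and then sets model terms for HbA1c and other efficacy analyses; it is silent on safety event models. SAP 6.5, without a safety exception: "country/pooled country will be used as a fixed effect in statistical analyses".

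In SAP 6.13 the default model for continuous safety measures includes country/pooled country, HbA1c category and metformin use. The default rate model, to be used where necessary, is a "generalized linear mixed-effects model assuming the number of events follow a negative binomial distribution, and including treatment as a fixed effect". Its only other component is the exposure term: "The logarithm of days during the active treatment period will be adjusted as an offset".

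The hypoglycemia rate has its own model in 6.13.2.1, also negative binomial with a log-days offset, but with the "mean modeled using country/pooled country, baseline metformin use (Yes/No), baseline HbA1c category, and treatment as fixed effects".

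For time to first event, SAP 6.13 says that for selected parameters a "time-to-first-event analysis via the Cox proportional hazards model may be conducted". For rescue therapy, given enough episodes, SAP 6.13.2.2 says "a time-to-first-event analysis for the initiation of rescue therapy will be conducted by treatment using a cox proportional regression model". Neither names a covariate or stratum.

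**The concern.** Stratified allocation balances the arms on factors expected to predict outcome. An analysis that leaves those factors out treats the variation they explain as residual noise. In a negative binomial model it goes into the dispersion and enlarges the standard error of the log rate ratio. Country is a plausible source of such variation, because adverse event reporting can differ between countries.

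The text also gives two answers to one question. Read by 6.5, a safety rate model contains country; read by 6.13, it does not. This is an open-label trial, and a model whose terms are unsettled leaves the analyst a choice that should be closed in advance. What is at stake is the precision of safety rate ratios, not the primary comparison or its error rate.

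**Working it through.** **The plan's own figures.** The documents give no rate, dispersion or interval width for any safety event, so there is no directly relevant figure to reproduce. The design power does reproduce with SD 1.3, margin 0.3 and one-sided 0.025:
- Each dose: 0.3/(1.3·√(1/197 + 1/591)) = 2.805; Φ(2.805 − 1.960) = 80.1%, against 80% stated.
- Pooled: 0.3/(1.3·√(2/591)) = 3.967; Φ(3.967 − 1.960) = 97.8%, against 97% stated.

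The arm sizes used below, 591 against 591, are therefore the plan's.

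**Assumed inputs.** μ = events per patient-year; k = dispersion within strata; s = SD of the log event rate explained by the randomisation factors; one year of follow-up.

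**Formulas for the SE of the log rate ratio.**
- Treatment only: √(2(1/μ + k_m)/591), with k_m = (1 + k)·exp(s²) − 1.
- Adjusted: √(2/(591·I)), with I the average over strata of μ_j/(1 + k·μ_j).

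Example, μ = 0.2, k = 2, s = 0.4: k_m = 3 × 1.1735 − 1 = 2.5205. Treatment-only SE = √(2 × 7.5205/591) = 0.1595. With I = 0.1383, adjusted SE = √(2/(591 × 0.1383)) = 0.1564. The treatment-only SE is 2.0% larger.

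Excess SE of the treatment-only model, for k from 1 to 4:

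| μ | s = 0 | s = 0.2 | s = 0.4 | s = 0.6 |
|---|---|---|---|---|
| 0.05 | 0% | 0.1% | 0.4–0.6% | 1.1–1.7% |
| 0.2 | 0% | 0.4–0.6% | 1.7–2.7% | 4.2–6.7% |
| 1 | 0% | 1.5–1.7% | 6.2–6.9% | 14.7–16.2% |
| 3 | 0% | 2.2–2.6% | 8.9–10.6% | 20.7–24.2% |

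**Simulation, rate model.** 300 trials per setting; 591 against 591; 15 assumed countries; stratified blocks of 6; 0.3 events per year; dispersion 2. Adjusted-to-unadjusted SE ratios were 0.991, 0.974 and 0.945 for between-country SDs of the log rate of 0.25, 0.5 and 0.75, so intervals 0.9%, 2.6% and 5.5% narrower. Adjusted coverage stayed at 94–96%. A separate simulation of about 150 trials per scenario, at 0.1 to 0.3 events per year, gave excess SEs of 0.3–0.4% with no prognostic effect, 0.9–1.2% with a moderate one and 1.9–3.7% with a strong one.

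**Formula against simulation.** At μ = 0.3, k = 2, s = 0.5: k_m = 3 × 1.2840 − 1 = 2.852; treatment-only SE = √(2 × (3.333 + 2.852)/591) = 0.1447; adjusted SE, with I = 0.177, is 0.1383. That is 4.4% narrower, against 2.6% simulated. The formula runs high when heterogeneity is large, so the larger table entries are better read as upper indications.

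**Simulation, Cox.** The unadjusted SE of the log hazard ratio was equal to or about 0.1% smaller than the adjusted SE in every scenario. With strong factors the estimate was attenuated (−0.339 against −0.358, a ratio of 0.947) and power was 66% against 75%. With about 150 trials each power figure has a Monte Carlo SE near 4 points (√(0.66 × 0.34/150) = 0.039). Attenuation alone would take 75% to Φ(0.947 × 2.634 − 1.960) ≈ 70%, so part of the nine-point gap may be noise; the direction is as expected.

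**The case against.** **The rate model may hardly be used.** It applies only where necessary. Hypoglycemia, the one event rate with its own model, is already adjusted. Injection site reaction rates (6.13.2.9) are to be summarised, and no model is promised. This stands: no analysis certain to run under the default has been identified, which keeps the point minor.

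**Section 6.5 cannot bind everything.** Fisher's exact test is the default for categorical safety responses and adjusts for nothing, and 6.3 prescribes terms only for efficacy. This stands in part. It shows 6.5 is worded too broadly, but leaves unexplained why two negative binomial rate models in one safety section differ.

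**Silence is not exclusion.** The model is called mixed-effects yet no random effect is named, so the list may simply be incomplete. If so, it should be completed.

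**The fallback gives up country, the factor most likely to matter.** True, but country uses the most parameters, and with rare events the gain from any adjustment is near zero.

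Three stronger readings are tempting, and the documents do not support them:
- That safety intervals in general are wider than the design allows. No event rates are given, and the loss vanishes when events are rare or the factors weak.
- That Cox intervals are too wide. Omitting covariates leaves the SE essentially unchanged; the cost is attenuation and power.
- That time to study drug discontinuation is an unadjusted Cox analysis. SAP 6.10.1 and 6.13.1.4 say only that a time-to-event analysis will be done, and Protocol 9.4.2.4 asks for Kaplan-Meier.

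**Conclusion.** The inconsistency is in the text and depends on no simulation: the default rate model omits the randomisation factors, conflicts with 6.5 on country, and departs from its neighbours in 6.13 and 6.13.2.1. The consequence is small. The treatment-only analysis is valid under stratified allocation, with no inflation of type 1 error. It loses roughly 1% to 5% of interval width at an assumed 0.3 events per year with modest to strong country differences, and close to nothing for rare events or weak factors. Excess SEs of 6% to 24% need about one or more events per patient-year and strongly prognostic factors, and no such event outside hypoglycemia is shown. These sizes rest on assumed rates, dispersions, country numbers and between-country spread. This is a worthwhile tidy-up, not a threat to any conclusion.

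**What to change.** In SAP 6.13, list the fixed effects of the default rate model as treatment, country/pooled country, baseline HbA1c category and baseline metformin use, matching 6.13.2.1. Prespecify a reduced model, for example without country, for when events are too few to fit. Tie the trigger to the total event count with arms combined, so that the choice does not depend on the treatment comparison. In the same edit, name the random effect or drop the mixed-effects label.

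For the Cox models in 6.13 and 6.13.2.2, where they are run, state the same covariates and the same fallback.

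If the sponsor prefers unadjusted safety event models, it should instead limit the 6.5 statement to the analyses it is meant to cover.

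The cost is a sentence or two in the SAP; the hypoglycemia rate model already has this structure. The one downside is the need for the sparse-event fallback.
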